**Table 8. Clinical Laboratory Tests**

Hematology	Clinical Chemistry	Additional Tests
Hematocrit	Blood Urea Nitrogen (BUN)	HBsAg b
Hemoglobin	Creatinine	Anti-HCV Ab b
Red Blood Cell (RBC) count	Total bilirubin a	Anti-HIV Ab b
White Blood Cell (WBC) count	Direct and indirect bilirubin	FSH (all females) b
Neutrophils	Serum glutamic-pyruvic	Urine and Serum Human
Bands, if detected	transaminase (SGPT/ALT)	Chorionic Gonadotropin
Lymphocytes	Serum glutamic-oxaloacetic	(hCG) females) c
Monocytes	transaminase(SGOT/AST)	HCV RNA
Basophils	Alkaline phosphatase	Total Insulin
Eosinophils	Sodium	IL28B b
Platelet count (estimate not acceptable)	Potassium	HCV genotype and subtype b
ANC	Calcium	Pharmacogenetic DNA
Prothrombin Time/INR a	Inorganic phosphorus	(optional)
Activated partial thromboplastin time (aPTT)	Uric acid	
Reticulocyte count	Cholesterol	
	Total protein	
	Glucose	
	Triglycerides	
	Albumin a	
	Chloride	
	Bicarbonate	
	Magnesium	
	Gamma-glutamyl transferase (GGT) d	
	Creatinine clearance (Cockcroft Gault calculation)	
	Alpha2-macroglobulin d	
	Haptoglobin d	
	Apolipoprotein A1 d	
	Alpha-Fetoprotein (AFP) b	
Urinalysis		
Specific gravity		
Ketones		
pH		
Protein		
Blood		
Glucose		
Urobilinogen		
Bilirubin		
Leukocyte esterase		
Microscopic (reflex)		

a. Also a component of the Child-Pugh Assessment.

b. Performed only at Screening.

c. Urine pregnancy testing is not required for female subjects who are confirmed to be post-menopausal or who have a documented history of prior bilateral tubal ligation, bilateral oophorectomy or hysterectomy.

d. Also a component of FibroTest.

For any laboratory test value outside the reference range that the investigator considers clinically significant:

- The investigator will repeat the test to verify the out-of-range value.

- The investigator will follow the out-of-range value to a satisfactory clinical resolution.
- A laboratory test value that requires a subject to be discontinued from the study, discontinued from study drug or requires a subject to receive treatment will be recorded as an adverse event.

The management of laboratory abnormalities that may occur during the study is described in Section 6.7.

### **Liver Biopsy, FibroScan or FibroTest**

At screening, subjects who have not had a liver biopsy within 24 months prior to screening, but who otherwise meet all of the inclusion criteria and none of the exclusion criteria will undergo either a liver biopsy or non-invasive test (FibroScan or FibroTest/APRI prior to enrollment) to determine presence or absence of cirrhosis. APRI should be calculated from samples drawn on the same day. Selection of liver biopsy or non-invasive testing should be based on local standard practice.

FibroScan (if available) and FibroTest will be performed as indicated in [Table 7](#).

### **Child-Pugh Score and Category**

The Child-Pugh score will be calculated prior to the Day 1 Visit and documented on the Screening Visit eCRFs for cirrhotic subjects only. Subjects who were considered to be non-cirrhotic at the Screening Visit but identified as cirrhotic (according to definitions listed in Section 5.1) during the screening period will return to the site prior to the Study Day 1 Visit for Child-Pugh assessment.

The Child-Pugh score uses five clinical measures of liver disease (3 laboratory parameters and 2 clinical assessments) and is applicable only to subjects with cirrhosis. Child-Pugh score will be determined at the Screening Visit as indicated in [Table 7](#). The Child-Pugh score will be automatically calculated prior to Day 1 by EDC RAVE once the investigator or designated site personnel enters the subject's parameters (as listed in [Table 9](#)). A total

score of 5 – 6 is considered Class A (compensated disease); 7 – 9 is Class B (significant functional compromise); and 10 – 15 is Class C (decompensated disease).

**Table 9. Child-Pugh Classification of Severity of Cirrhosis**

Parameter	Points Assigned for Observed Findings		
	1	2	3
Total bilirubin, $\mu\text{mol/L}$ (mg/dL)	< 34.2 (< 2)	34.2 – 51.3 (2 – 3)	> 51.3 (> 3)
Serum albumin, g/L (g/dL)	> 35 (> 3.5)	28 – 35 (2.8 – 3.5)	< 28 (< 2.8)
INR	< 1.7	1.7 – 2.3	> 2.3
Ascites*	None	Slight	Moderate to severe
Hepatic encephalopathy**	None	Grade 1 or 2 (or suppressed with medication)	Grade 3 or 4 (or refractory)

\* None.

Slight ascites = Ascites detectable only by ultrasound examination.

Moderate ascites = Ascites manifested by moderate symmetrical distension of the abdomen.

Severe ascites = Large or gross ascites with marked abdominal distension.

\*\* Grade 0: normal consciousness, personality, neurological examination, electroencephalogram.

Grade 1: restless, sleep disturbed, irritable/agitated, tremor, impaired handwriting, 5 cps waves.

Grade 2: lethargic, time-disoriented, inappropriate behavior, asterixis, ataxia, slow triphasic waves.

Grade 3: somnolent, stuporous, place-disoriented, hyperactive reflexes, rigidity, slower waves.

Grade 4: unarousable coma, no personality/behavior, decerebrate, slow 2 to 3 cps delta activity

### **Clinical Assessment of Liver Decompensation**

A clinical assessment of hepatic encephalopathy and ascites will be performed at Study Day 1 prior to dosing to confirm the subject has not progressed to hepatic decompensation since screening for all subjects who have compensated cirrhosis. Grading system guidelines for ascites are listed above in [Table 9](#).

### **Liver Ultrasound**

In order to monitor for the presence of hepatocellular carcinoma (HCC) an ultrasound of the liver will be performed as indicated in [Table 7](#).

For subjects with compensated cirrhosis:

- Subjects receiving 12 weeks of treatment will have a liver ultrasound performed at the Screening Visit and all post-treatment visits except PT Week 4
- Subjects receiving 24 weeks of treatment will have a liver ultrasound performed at the screening visit, Week 24 visit, and all post-treatment visits except the PT Week 4 and PT Week 12.

For subjects without cirrhosis: Liver ultrasound will be performed at the screening visit, PT Week 52, PT Week 156 and PT Week 260.

Subjects with a historical negative liver ultrasound, CT or MRI (within 3 months prior to screening) are not required to undergo a screening ultrasound.

A positive ultrasound result suspicious for HCC at screening will be confirmed with CT scan or MRI during the screening period. Suspicious ultrasound lesions confirmed by CT or MRI are exclusionary.

A positive Ultrasound result suspicious for HCC during the treatment or post-treatment period will be confirmed with CT scan or MRI.

### **Assessment of Clinical Outcomes**

The following clinical outcomes will be assessed during the study:

- All-cause death: death due to any cause
- Liver-related death: death as the result of a liver-related cause
- Liver decompensation: development of any of the following conditions: ascites, hepatic encephalopathy or variceal bleeding

- Liver transplantation: any subject who had a liver transplantation
- Hepatocellular carcinoma (HCC): development of HCC in any subject at any time during the study. HCC is defined by histologic confirmation or a > 1 cm mass lesion on cross-sectional imaging that meets the diagnostic criteria for HCC according to EASL guidelines.
- Composite of any of the above outcomes

Clinical Outcome events that occur during the Treatment Period through Post-Treatment Week 4 are to be recorded and documented in the eCRF as an AE/SAE (Section 6.0) in addition to being captured in the Clinical Outcome eCRF(s). Clinical Outcome events that occur after Post-Treatment Week 4 are considered a progression of the subject's existing liver disease and are to be recorded in the Clinical Outcome eCRFs only, except when the clinical outcome is death, in which case the AE/SAE eCRF would also need to be completed. This information may be collected over the telephone in the event the subject is unable to return to the investigative site.

An independent outcome committee will review and adjudicate the validity of each clinical outcome.

### **Concomitant Medication Assessment**

Use of medications (prescription or over-the-counter, including vitamins and herbal supplements) from the time of signing the consent through 30 days after last dose of study drug will be recorded in the eCRF at each study visit indicated in Table 7. The investigator or qualified designee should review the locally approved labels for concomitant medication(s), ribavirin and ritonavir and, where applicable, ABT-450, ABT-267, and ABT-333 and should also utilize the DDI tool that will be provided by the sponsor for potential drug interactions. The investigator or qualified designee should document their DDI review in the subject's source or print report and place in subject's source documents.

During the Post-Treatment Period, all medications will be collected until 30 days following the last dose of study drugs. Only anti-HCV medications and concomitant medications relevant to SAE of death will be collected thereafter.

### **Patient Reported Outcomes (PRO) Instruments (Questionnaires)**

Subjects will complete the self-administered PRO instruments (where allowed per local regulatory guidelines) on the study days specified in [Table 7](#). Subjects will be instructed to follow the instructions provided with each instrument and to provide the best possible response to each item. Site personnel shall not provide interpretation or assistance to subjects other than encouragement to complete the tasks. Subjects who are functionally unable to read or understand any of the instruments may have site personnel read the questionnaires to them. Site personnel will encourage completion of each instrument at all applicable visits and will ensure that a response is entered for all items.

PRO instruments will be consistently presented so that subjects will complete the Short-Form 36 Version 2 health survey (SF-36v2) instrument first and the FACIT-F instrument second. PRO instruments should be completed as of the first study procedure at each visit and prior to any discussion of adverse events or any review of laboratory findings, including HCV RNA levels.

### **Short Form 36 – Version 2 Health Survey (SF-36v2)**

The SF-36v2 is a non-disease specific Health Related Quality of Life (HRQoL) instrument with extensive use in multiple disease states. The SF-36v2 instrument comprises 36 total items (questions) targeting a subject's functional health and well-being in 8 domains (physical functioning, role physical, bodily pain, general health, vitality, social functioning, role emotional and mental health) with a recall period of 4 weeks. Domain scores are aggregated into a Physical Component Summary score and a Mental Component Summary score. Higher SF-36v2 scores indicate a better state of health. Completion of the SF-36v2 should require approximately 10 minutes.

### **The Functional Assessment of Chronic Illness Therapy – Fatigue (FACIT–F)**

The FACIT–F is a symptom specific instrument with a focus on measuring fatigue in a variety of chronic diseases or health conditions. It was originally developed from interviews with oncology patients and clinical experts to assess anemia-associated fatigue. Its 13-item version assesses peripheral, central, or mixed fatigue with a recall period of 7 days and yields a summed total score ranging between 0 and 52. Higher FACIT–F scores indicate a lesser degree of fatigue. Completion of the FACIT–F (version 4) should require approximately 5 – 10 minutes.

### **Assignment of Subject Numbers**

A subject number is assigned at screening via IRT. Subjects enrolled in the study will continue with the same subject number assigned at screening. Subject numbers will be unique 5-digit numbers and will begin with 10001.

### **Study Drug Dispensation:**

Study drugs will be dispensed at the visits as indicated in [Table 7](#).

### **Study Drug Returned for IRT Reconciliation**

At each visit noted in [Table 7](#), study drug compliance per the number of tablets of ABT-450/r/ABT-267, ABT-333, and RBV (if applicable) remaining in each kit (blister card for DAAs or bottle for RBV) will be recorded in the IRT system. Additional information regarding treatment compliance can be found in [Section 5.5.7](#).

### **HCV Genotype and Subtype**

Plasma samples for HCV genotype and subtype will be collected at Screening. Genotype and subtype will be assessed using the Versant® HCV genotype Inno-LiPA Assay, version 2.0 or higher (LiPA; Siemens Healthcare Diagnostics, Tarrytown, NY). Only subjects with HCV genotype 1 infection will be allowed to enroll.

### **HCV RNA Levels**

Plasma samples for HCV RNA levels will be collected as indicated in [Table 7](#). Plasma HCV RNA levels will be determined for each sample collected by the central laboratory using the COBAS® AmpliPrep/COBAS® TaqMan® HCV Test, v2.0. For this assay the lower limit of quantification (LLOQ) is 15 IU/mL.

### **HCV Resistance Testing Sample**

A plasma sample for HCV resistance testing will be collected at the study visits as indicated in [Table 7](#). Specific instructions for preparation and storage of HCV RNA and HCV resistance samples will be provided by the central laboratory, the Sponsor, or its designee.

### **Archive Samples**

Archive plasma and serum samples will be collected at the study visits, indicated in [Table 7](#). Archive samples are being collected for possible additional analyses, including but not limited to, study drug or metabolite measurements, viral load, safety/efficacy assessments, biomarkers of inflammation, HCV gene sequencing, HCV resistance testing, and other possible predictors of response, as determined by the Sponsor.

Specific instructions for preparation and storage of archive samples will be provided by the central laboratory, the Sponsor, or its designee.

## **5.3.1.2 Blood Samples for Pharmacogenetic Analysis**

### **IL28B Sample**

One (required) 4mL whole blood sample for deoxyribonucleic acid (DNA) isolation will be collected from each subject at screening for Interleukin 28B (IL28B) pharmacogenetic analysis and related markers. If the sample is not collected at this visit, it may be collected at any time throughout the study. This sample will not be used for any testing other than IL28B genotypes.

Specific instructions for sample collection, preparation and storage will be provided by the central laboratory, the Sponsor, or its designee. Samples will be used only for IL28B testing and then destroyed.

### **Optional Pharmacogenetic Sample**

One 4 mL whole blood sample for DNA isolation will be collected on Day 1 from each subject who consents to provide a sample for pharmacogenetic analysis. The procedure for obtaining and documenting informed consent is discussed in Section 9.3. If the sample is not collected on Day 1, it may be collected at any time throughout the study.

The sample collection tubes will minimally be labeled with "PG-DNA," protocol number, and subject number. Samples will be shipped frozen to AbbVie or a designated laboratory for DNA extraction and long-term storage. Instructions for the preparation and shipment of pharmacogenetic samples will be provided in the lab manual.

AbbVie will store the DNA samples in a secure storage space with adequate measures to protect confidentiality. The samples will be retained while research on ABT-450/r/ABT-267, ABT-333 (or drugs of this class) continues but no longer than 20 years.

### **5.3.1.3 Meals and Dietary Requirements**

All study drugs should be dosed together and administered with food, i.e., the AM dose of ABT-450/r/ABT-267, ABT-333 and RBV (if applicable) should be taken together with food and the PM dose of ABT-333 and RBV (if applicable) should be taken with food.

### **5.3.2 Efficacy Variables**

#### **5.3.2.1 Primary Variable**

The primary endpoint is the incidence of all-cause death, liver-related death, liver decompensation, liver transplantation, hepatocellular carcinoma, and the composite of any of the above outcomes observed during the post-treatment period.

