### **8.1.2 Efficacy**

The primary efficacy analysis on clinical outcomes will be performed on all subjects in the ITT population. All other efficacy analyses will be performed on the ITT-I population

At sites where FibroScan is available, subjects will have FibroScan® performed at Screening, End-of-Treatment Visit and throughout the Treatment and Post-Treatment Period as indicated in [Table 7](#) for the purpose of assessing changes in liver fibrosis over time.

Incidence of all-cause death, liver-related death, liver decompensation, liver transplantation, and hepatocellular carcinoma as defined in protocol Section [5.3.1.1](#) will be collected during the 5-Year Post-Treatment Period.

Plasma HCV RNA levels will be determined for each sample collected by the central laboratory using the COBAS® AmpliPrep/COBAS® TaqMan® HCV Test, v2.0. For this assay, the lower limit of quantification (LLOQ) is 15 IU/mL. HCV RNA results that are detectable but not quantifiable are reported as "HCV RNA is detected, less than 15 IU/mL HCV RNA".

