10.0 Efficacy Analysis

10.1 General Considerations

The primary efficacy analysis on clinical outcomes will be performed on all subjects in the ITT population as defined in Section 5.1. All other efficacy analyses will be performed on the ITT-I population.

Treatment effects will be evaluated based on a two-sided significance level of 0.05 (when rounded to three decimal places). The data from the ITT-I population will be presented in one column/row as it represents the labelled treatment.

Plasma HCV RNA levels will be determined for each sample collected by the central laboratory using the COBAS[®] AmpliPrep/COBAS[®] TaqMan[®] HCV Test, v2.0. For this assay, the lower limit of quantification (LLOQ) and the lower limit of detection (LLOD) is 15 IU/mL. HCV RNA results that are detectable but not quantifiable are reported as "< 15 IU/mL" and results that are not detectable are reported as "NON-DETECTED."

Assessment of Clinical Outcomes

Incidence of the following clinical outcome events will be collected during the 12/24 weeks of treatment and the 5-year (PT Week 260) Post-Treatment Period. Data will be adjudicated by an independent outcome committee and results will be reported in the "Clinical Outcome" eCRFs:

- All-cause death: Death due to any cause.
- Liver-related death: Death as the result of a liver-related cause.
- Liver decompensation: Development of any of the following conditions: ascites, hepatic encephalopathy, or variceal bleeding.
- Liver transplantation: any subject who had a liver transplantation.

- Hepatocellular carcinoma (HCC): development of HCC in any subject at any time during the study. HCC is defined by histologic confirmation or a > 1 cm mass lesion on cross-sectional imaging that meets the diagnostic criteria for HCC according to EASL guidelines.
- Composite of any of the above outcomes.

Definitions for HCV RNA Efficacy Endpoints

Note that a confirmed quantifiable post-treatment value is defined as two consecutive post-treatment HCV RNA measurements \geq LLOQ. During treatment, a confirmed quantifiable value is defined as any two consecutive HCV RNA values \geq LLOQ, either both during treatment or at the final treatment measurement and the next consecutive post-treatment measurement.

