10.3 Primary Efficacy Analysis

The primary efficacy analysis will be conducted among subjects in the ITT population as described in Section 5.1. HCV RNA values and SVR₁₂ will be imputed as described in Section 6.3.

The primary efficacy endpoint is to assess the effect of response to treatment (as assessed by SVR₁₂ status) on clinical outcomes by comparing the time to incidence of the following events between subjects who achieve SVR₁₂ and those who do not.

- All-cause death
- Liver-related death
- Liver decompensation
- Liver transplantation
- Hepatocellular carcinoma
- Composite of any of the above outcomes

For each of the six event types as listed above, a subject's time to event will be defined as the number of days from the first day of study drug to the day the subject experiences an event of interest. All events of interest will be included, regardless of whether the event occurred while the subject was still taking study drug or had previously discontinued study drug. However, events occurred after a subject started another treatment for HCV will be excluded and the subject will be censored at the time of starting the new HCV treatment. If the subject has not experienced an event of interest nor has the subject died (all-cause death), the subject's data will be censored at the date of the subject's last available assessment of clinical outcomes. All-cause death is a censoring event for liver-related death, liver decompensation, liver transplantation and hepatocellular carcinoma. For subjects with no post-baseline assessment, the subject's data will be censored on the first day of study drug. Time to the composite of clinical outcomes is the time to the first occurrence of any clinical outcome.

For each of the six event types, the distribution of time to event will be estimated for subjects who have achieved SVR₁₂ and those who haven't using Kaplan-Meier methodology and compared between the subjects who have achieved SVR₁₂ and those who haven't using the log-rank test.

For each of the six event types, the 1-, 2-, 3-, 4-, and 5-year event-free survival rate will be estimated using Kaplan-Meier methodology and a 95% confidence interval will be constructed separately for those who have achieved SVR₁₂ and those who haven't.

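### Protocol 5.3.2.1 restricts the primary endpoint to post-treatment outcomes, while the SAP counts events from first dose; the counting period and time origin need one consistent statement

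*Protocol*

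**What the plan says.** **Post-treatment only.** Protocol 5.3.2.1, the section that defines the primary variable, ends with "the composite of any of the above outcomes observed during the post-treatment period". Protocol 8.1.2 says that the incidence of the five outcomes "will be collected during the 5-Year Post-Treatment Period". By the protocol's definition of terms, the Treatment Period runs from Day 1 through the last dose, and the Post-Treatment Period begins the day after.

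**Treatment included.** SAP 10.1 says that the events "will be collected during the 12/24 weeks of treatment and the 5-year (PT Week 260) Post-Treatment Period". SAP 10.3 measures time as "the number of days from the first day of study drug to the day the subject experiences an event of interest" and adds: "All events of interest will be included, regardless of whether the event occurred while the subject was still taking study drug".

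**Protocol text nearer the SAP.** The synopsis and Protocol 5.1.2 have clinical outcomes assessed during treatment. Protocol 5.3.1.1 (Assessment of Clinical Outcomes) sends on-treatment events to the Clinical Outcome eCRF and accepts HCC at any time in the study. Protocol 6.1.1 says these outcomes form part of the study endpoints. Protocol 8.1.2.1, which describes the Cox comparison, names no period.

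**Scan schedule.** For cirrhotic subjects, Protocol 5.3.1.1 (Liver Ultrasound) reads "Subjects receiving 24 weeks of treatment will have a liver ultrasound performed at the screening visit, Week 24 visit", followed by the post-treatment visits other than PT Weeks 4 and 12. Those on 12 weeks of treatment have their first follow-up scan at PT Week 12, which is the same study week.

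**The concern.** The two rules give different event sets for decompensation, transplantation, HCC, death and the composite.

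The difference bears on interpretation because the exposure is SVR12 status, which is fixed only about 12 weeks after the last dose. A decompensation or HCC during treatment cannot result from SVR12. It can lead to early stopping, and SAP 10.1 lists premature discontinuation among the reasons for SVR12 non-response. SAP 6.3 also imputes a subject still lacking an SVR12 value as a failure. Counting such events can therefore credit to non-SVR12 something that came before it and helped cause it. The non-SVR12 group is assumed to be 4% of subjects, so a few events carry weight.

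The time origin matters too. SAP 10.3 tests event-free survival at Year 5. From first dose, 260 weeks is PT Week 248 on the 12-week regimen (260 − 12) or PT Week 236 on the 24-week regimen (260 − 24). From last dose it is PT Week 260.

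**Working it through.** **Inputs** (Protocol 8.2, SAP 4.3): N = 2000, 4% non-SVR12 (80 against 1920 subjects), 20% five-year composite rate in non-SVR12, hazard ratio 0.25, dropout up to 20%. Follow-up from first dose is 272 or 284 weeks (SAP 4.2). A constant hazard is my assumption.

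**The plan's own figure.** The non-SVR12 hazard is −ln(0.8)/5 = 0.0446 per year and the SVR12 hazard is 0.25 × 0.0446 = 0.0112. The five-year SVR12 rate is 1 − 0.8^0.25 = 5.43%. Events over five years are 80 × 0.20 + 1920 × 0.0543 = 16.0 + 104.2 = 120.2. Schoenfeld power is 84.6% without dropout, and 80.6% (107.9 events) with 20% exponential dropout over five years. The stated power above 80% reproduces.

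**Share of composite events on treatment.** Expected events are n(1 − exp(−ht)), with t equal to the treatment weeks for the numerator and total follow-up for the denominator. There is no dropout, and deaths are included.

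| Regimen mix | On treatment | Total | Share |
|---|---|---|---|
| All 12 weeks | 5.8 | 125.5 | 4.6% |
| 276 of 2000 on 24 weeks | 6.5 | 126.2 | 5.2% |
| All 24 weeks (limit only) | 11.5 | 130.8 | 8.8% |

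The 276 is 69% of the cap of about 400 cirrhotic subjects in this study. The 69% is an assumption, close to the 68.7% GT1a in the cirrhosis study M13-099 (Protocol 3.0). With 20% dropout the first and last shares become 5.1% and 9.8%.

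**Effect on power.** With dropout, Schoenfeld power under the SAP rule against post-treatment only is 82.0% against 80.0% (all 12 weeks) and 83.4% against 79.5% (all 24 weeks). A simulated log-rank test gives 97–98% throughout.

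**Effect on the hazard ratio.** With 12 weeks of treatment, expected events are 16.7 in non-SVR12 over 373 person-years and 108.8 in SVR12 over 9756 person-years. Suppose k on-treatment events fall in the non-SVR12 group because they led to stopping drug:

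- k = 0: (108.8/9756)/(16.7/373) = 0.25
- k = 1: (107.8/9756)/(17.7/373) = 0.234
- k = 2: 0.219
- k = 3: 0.206

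The documents give no value for k. If on-treatment events instead split 96:4 in line with group size, the crude hazard ratio moves to about 0.26, slightly toward the null.

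**HCC at the Week 24 scan.** Cases = 400 × share on 24 weeks × annual rate × 24/52. With assumed shares of 30–69% and rates of 1–3% (3% is the figure for cirrhosis in Protocol 3.0), the low end is 400 × 0.30 × 0.01 × 24/52 = 0.6 and the high end is 400 × 0.69 × 0.03 × 24/52 = 3.8. This is an upper bound on the cases that could switch between the two rules.

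**The case against.** The best reply is that nothing is ambiguous in practice. SAP 4.4 says that analyses follow the SAP, SAP 10.3 is explicit, and much of the protocol points the same way. Protocol 8.1.2 is a statement about collection, not a definition. A reader might infer a clean split between protocol and SAP; the documents do not support that. What stands against the reply is that Protocol 5.3.2.1 defines the primary variable, names a period, and is contradicted without comment.

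Three stronger inferences also fail.

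- *Up to 9% of events are affected.* The 8.8% puts every subject on 24 weeks. Only GT1a (or unknown or mixed subtype) cirrhotic subjects are assigned to that, under the cap. A share well above 5% needs events to concentrate in that subgroup. Excluding prior decompensation and confirmed HCC, with a Day 1 recheck in cirrhotic subjects, may push the share lower.
- *The Week 24 HCC cases count under one rule only.* HCC needs histology or qualifying cross-sectional imaging, and Week 24 is the end-of-treatment visit. Confirmation may come after the last dose, and no dating rule is given.
- *The bias must favour SVR12.* It may, through early stopping, but no such bias arises if the events are unrelated to SVR12 status. Either shift is small against an approximate 95% interval of 0.15–0.42, from 16 and 104 expected events.

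It is also fair to say that moving to post-treatment events does not fully restore the time order. Events between the last dose and the SVR12 window (days 57–126) also precede SVR12 status.

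**Conclusion.** The inconsistency is real and concerns the primary endpoint: Protocol 5.3.2.1 and SAP 10.1 and 10.3 cannot both be followed, and the protocol does not settle the matter itself. Under the plan's inputs and a constant hazard, the disputed share is roughly 5% of composite events, deaths included; no separate non-fatal figure can be derived from the documents. The effect on power is small. The effect on the hazard ratio is possible and plausibly in favour of SVR12, at 0.23–0.21 against 0.25 if one to three on-treatment events led to non-SVR12, but that rests on an assumed number of events. It should be resolved before the primary analysis, as a matter of a clearly stated endpoint rather than a demonstrated bias.

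**What to change.** 1. State one counting period and one time origin, in the same words, in Protocol 5.3.2.1, 8.1.2 and 8.1.2.1 and in SAP 10.1 and 10.3.
2. State how HCC onset is dated: at the first suspicious scan or at confirmation.
3. Report the comparison under both counting rules, naming one as primary and the other as a sensitivity analysis.
4. In the post-treatment-only version, do not count on-treatment non-fatal events, but keep those subjects in the analysis so that their later post-treatment deaths and other new outcomes count, as Protocol 5.3.2.1 implies. Removing the subjects would drop such deaths and depart from the ITT population.
5. Tabulate by SVR12 status the events during treatment and, separately, those between the last dose and the SVR12 window.

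The cost is wording, one extra run and one table. The post-treatment-only version has about 5% fewer events. The data are already collected under both documents.
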